3.2 Collaborator(s)/External partner(s)/Committee(s)

CCI [redacted]	Consultant Urologist	CCI [redacted] [redacted] [redacted]	Principle Investigator
----------------	----------------------	--	------------------------

CCI [redacted]	Senior Researcher	CCI [redacted] [redacted]	Senior statistician

4. Abstract

Acronym/Title	PRostAte Cancer vTe In SwEden: epidemiology and anticoagulation treatment of VTE PRACTISE
Protocol version and date	1.0, 12 May 2019
IMPACT study number	20653
Study type / Study phase	Observational, Phase IV
Author	CCI
Rationale and background	
Patients with cancer are at a significantly increased risk of experiencing a venous thromboembolism (VTE). VTE is defined by deep vein thrombosis (DVT) or pulmonary embolism (PE) and is a leading cause of morbidity and death among cancer patients. A variety of anti-coagulants are available to treat VTE with treatments differing between cancer and non-cancer patients. The use of such treatments has changed over time with a shift towards the increased use of non-vitamin K oral anticoagulants (NOACs) due to their ease of administration.
 
An increasing success of cancer treatments results in significant extension of survival, even in cases of metastatic diseases; therefore prevention of debilitating thrombotic events in these patients is gaining importance. Although prostate cancer (PCa) belongs to the cancer types with a relatively low risk of VTE, the burden of patients with PCa is high (the commonest cancer type in men); thus adequate treatment and secondary prophylaxis of VTE in this population is of clinical and public health importance.

Research question and objectives	
This study aims to identify the current landscape of VTE events and its treatment in prostate cancer (PCa) patients in Sweden.
 
The objectives include:
 
Primary objective
 
Among all men with PCa:
 
 1. To describe socio-demographic and clinical characteristics at the date of an incident PCa diagnosis. 2. To estimate the occurrence of cancer-related VTE. 3. To describe the cancer therapies in PCa at the initial

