Non-interventional observational research data originating from cancer cohorts can provide relevant real-world clinical evidence and would be important complementing data from RCT's . As cancer patients are very heterogeneous in their clinical characteristics, it would be extremely difficult to construct a trial addressing all questions of interest; hence an observational study design based on data from clinical practice will provide a deeper understanding the consequences of current clinical practice for anticoagulation approaches in treatment of cancer patients and how the choice of a regimen influences risk of thrombotic and bleeding events. Generated evidence will support physicians in their treatment decisions.

Sweden offers a unique opportunity to study routine clinical practice and associated outcomes in cancer patients as notification of cancer has been mandatory in all Nordic countries for decades, and the Swedish Cancer Registry was established already in 1958. The completeness of data on incident cases is considered to be very high.

The study will focus on prostate cancer (PCa), the most common cancer form in men. It will be based on the data from the Prostate Cancer Database Sweden (PCBaSe), containing information from many national registries other than the Cancer register, such as Patient register, Dispensed drug register, Cause of Death registry and Population registries. In total, over 180,000 newly diagnosed cases of PCa in Sweden between 1996 to 2017 (currently available) together with a random sample of about 900,000 men from the general population without PCa in the same age group and area of residence as prostate cancer cases, are included into the PCBaSe.

8. Research questions and objectives

This study aims to identify the current landscape of VTE events and its treatment in prostate cancer (PCa) patients in Sweden.

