9.2.2 Study time frame

The study will capture the observation period of 2007-2016, hence focusing on the period when the Prescribed Drug Registry became available.

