9.2.3 Selection criteria from PCBaSe

PCa patients

Inclusion criteria

Initially all patients newly diagnosed with PCa between 2007-2016 with at least one year before the end of follow up date (31 December 2017) will be included.

From this population, a sub-population of PCa patients with a first cancer-related VTE event will be selected.

Exclusion criteria

No exclusions will be made.

Men without PCa

Inclusion criteria

All PCa-free men included in PCBaSe who are randomly selected from the general population of Sweden with the same birth year and county of residence of PCa patients diagnosed between 2007-2016.

Exclusion criteria

A PC free men diagnosed with a prostate cancer during the follow up will be identified and censored.

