9.4 Follow up

9.4.1 Exposure to anticoagulants

The exposure to AC treatment will be defined in two ways:

- the first is by following the patients until the end of the follow-up time, regardless if they are still on the drug or not.
- the second way is to follow up the patients until the filled prescription for each respective drug expires (“on/treatment”).

A grace period of 90 days will be used to define a new prescription of anticoagulant. The duration of a prescription will be derived from the median number of days between consecutive respective prescriptions after the grace period has passed.

The treatment exposure can then be used to study the switching of treatments and the discontinuation of treatments.

A start date will be defined as the date of the dispensed prescription for patients receiving anticoagulation.

Patients will be censored at earliest date of:

- Time of first occurrence of a recurrent VTE event or a bleeding event (major bleeding event i.e. intracranial, gastrointestinal, urogenital bleeding, or other bleeding leading to hospitalisation) or death
 - Patients will be followed until occurrence of one of the above mentioned outcomes of interest; similarly, the analysis is repeated in the same way for the other outcomes of interest. Therefore, the patients were not censored at the first outcome of interest and outcomes on treatment after the first is also taken in to account. Only first-time events of the same type are considered.
- End of observation time (data lock point for the database at 31st October 2017)
- Treatment discontinuation
- Treatment switching patients who switched will be censored at the time of the date of a filled prescription from a pharmacy of the new drug.

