9.8 Data analysis

Descriptive statistics will be used to define the socio-demographic and clinical characteristics (including main types of cancer therapies) of all PCa patients at the time of PCa diagnosis (Objective 1 and 3) and PCa-free men at the time of inclusion in PCBaSe (Objective 8) and include variables of interest listed above.

All categorical variables will presented by counts and proportions and continuous variables by mean, standard deviation, range, median, and first and third quartiles.

The occurrence will be estimated by calculating an incidence rate (accompanied by 95% CI) of cancer-related VTE events, split into PE and DVT events, in men with PCa (Objective 2) and in PCa-free men (Objective 10). The incidence rate is defined as the number of events of interest divided by the total number of person-years at risk. In men with PCa, the person-time at risk will be calculated from date of incident PCa diagnosis up until an outcome of interest, death or end of follow-up, whichever came first. The occurrence will be also described by Kaplan-Meier curves in different strata within different time-periods.

The AC treatment received by the PCa patients after a first cancer-related VTE event on an out-patient long-term basis will be reported by type of anticoagulation (LMWH, VKAs and NOACs) and its estimated duration (from the time-point of a hospital discharge up to 3 months, 3-6 months, more than 6 months) (Objective 4).

Time at risk for Objectives 5, 6 and 7 (recurrent VTE, bleeding leading to hospitalisation or death) will be calculated from first cancer-related VTE (the time-frame of defining cancer-relatedness will be specified later) for each events of interest up until event, death or end of follow-up.

The 95% CI for the incidence rate will be calculated using the Poisson distribution.

Incidence rates of recurrent VTE, bleedings and death will be calculated by the type and duration of AC treatment (stratification variables); however no comparative analysis of outcomes in three sub-groups of AC treatments, is planned.

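### Anticoagulant choice (Objective 4) is reported without any calendar split over 2007–2017, so the NOAC share will fall below the current use that the study aims to describe

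*Protocol*

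**What the plan says.** The Abstract and section 8 state the aim: "This study aims to identify the current landscape of VTE events and its treatment in prostate cancer (PCa) patients in Sweden". The Abstract's rationale adds: "The use of such treatments has changed over time with a shift towards the increased use of non-vitamin K oral anticoagulants (NOACs". Section 9.2.2 sets the period: "The study will capture the observation period of 2007-2016". Follow-up runs into 2017, with two end dates given: section 9.2.3 has "before the end of follow up date (31 December 2017" and section 9.4.1 has "End of observation time (data lock point for the database at 31st October 2017".

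For Objective 4, section 9.8 says that out-patient treatment "will be reported by type of anticoagulation (LMWH, VKAs and NOACs) and its estimated duration", in bands of up to 3, 3–6 and more than 6 months. For Objectives 5 and 7 it says: "Incidence rates of recurrent VTE, bleedings and death will be calculated by the type and duration of AC treatment (stratification variables". Time at risk for these objectives starts at the first cancer-related VTE and ends at the event, death or end of follow-up. Section 9.4.1 defines exposure in two ways: to the end of follow-up whether or not the drug is still taken, and on-treatment. Section 9.8 plans no comparative analysis of the three drug classes.

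**The concern.** The aim concerns practice now, and the protocol itself says that practice changed during the period studied. The reporting described for Objective 4 names drug class and duration but no calendar period or restriction to recent years. A single class distribution over roughly a decade mixes years before and after the shift, and its NOAC share would be quoted as the answer to a question about current treatment.

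A second effect follows for Objectives 5 and 7. If NOAC users have later index VTEs, they have shorter potential follow-up than other users. A rate of events per person-year, taken to the end of follow-up, then averages over different stretches of time since VTE in the different classes. Whether that matters depends on the shape of the hazard.

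**Working it through.** **1. Where calendar time appears.** Section 9.8 mentions time-periods once, undefined, for the Kaplan–Meier curves of VTE occurrence in men with and without prostate cancer. Neither the paragraph on Objective 4 nor the one on rates by treatment mentions them. The protocol states no pooled share or class rate to reproduce, so the sizes below rest on assumptions.

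**2. Pooled NOAC share (Objective 4).** Assumptions: the share is zero to 2011, then F × k/6 for k = 1 to 6 (2012 to 2017), where F is the 2017 share. Yearly counts of index VTEs are either flat (weight 1) or growing linearly (weights 1 to 11). Pooled share = Σ(weight × share) / Σ weight.

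- Flat: F × (1+2+3+4+5+6)/6 ÷ 11 = F × 3.5/11 = 0.318 F.
- Growing: F × (6×1+7×2+8×3+9×4+10×5+11×6)/6 ÷ 66 = F × 32.67/66 = 0.495 F.

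| 2017 share F | Pooled, flat | Pooled, growing | 2015–2017 only, flat |
|---|---|---|---|
| 40% | 12.7% | 19.8% | 33.3% |
| 60% | 19.1% | 29.7% | 50.0% |
| 80% | 25.5% | 39.6% | 66.7% |

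The last column is F × (4+5+6)/(3×6) = 0.833 F. If index VTEs stop at the end of 2016, the pooled share is 0.30 (flat: 15/5 ÷ 10) to 0.47 (growing: 130/5 ÷ 55) of the 2016 share, so the choice of end year hardly matters.

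**3. Potential follow-up under the same uptake.** Mid-year entry and follow-up to the end of 2017 give 5.5, 4.5, …, 0.5 years for entry in 2012 to 2017. With flat counts the NOAC mean is (1×5.5+2×4.5+3×3.5+4×2.5+5×1.5+6×0.5)/21 = 45.5/21 = 2.2 years. With growing counts it is 1.9 years. Non-NOAC users have 4.3–6.6 years across the scenarios.

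**4. Rates under identical hazards (Objectives 5 and 7, to end of follow-up).** Assumptions: the same hazard in every class, h1 for the first c = 0.25 years and h2 = 5 per 100 person-years (PY) afterwards; no deaths; entry spread evenly within each year. For follow-up T > c:

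- Expected events = 1 − exp(−h1·c − h2·(T−c)).
- Expected person-years = (1 − exp(−h1·c))/h1 + exp(−h1·c)·(1 − exp(−h2·(T−c)))/h2.

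For example, with h1 = 40 per 100 PY and T = 2, events are 0.1710, person-years 1.7541 and the rate 9.7 per 100 PY. Summing both quantities over entry dates, weighted by class share:

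| Hazard per 100 PY | NOAC rate | Non-NOAC rate | Ratio |
|---|---|---|---|
| 40, then 5 | 9.4–9.8 | 6.6–7.4 | 1.33–1.41 |
| 20, then 5 | 6.8–7.0 | 5.7–6.0 | 1.17–1.20 |
| 5 throughout | 5.0 | 5.0 | 1.00 |

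A second set of assumptions (late hazard 3 per 100 PY, higher hazard for the first 6 months, death at 10 per 100 PY, NOAC use starting in 2012 to 2014, follow-up to October 2017) gives NOAC to VKA ratios of 1.06–1.16 when the early hazard is twice the late one, 1.15–1.40 at four times, 1.21–1.57 at six times and 1.00 when constant. The upper ends compare NOAC starters with VKA starters who entered only before NOAC use began.

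**The case against.** **Calendar split.** Section 9.8 names type and duration but does not say that they are the only strata, and further breakdowns are often left to a statistical analysis plan. Objective 4 itself does not say current, and section 9.2.4 presents the results as representative of the period observed. A pooled table does describe that period. This limits the point: a reader might infer that the protocol rules out a calendar breakdown, and it does not. What stands is that the reporting it does set out does not answer the aim it states.

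**Class rates.** Much of the objection stands here. A reader might infer that each class receives one average rate. It does not: the rates are by class and duration band, section 9.4.1 adds an on-treatment definition with censoring at discontinuation and switching, and Objective 6 gives time to recurrence separately. All of this reduces the imbalance in follow-up. Duration of treatment is still not the same as time since VTE, and the definition running to the end of follow-up is kept.

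A reader might also set half a year of NOAC follow-up against five years for other drugs. With the hazards above that gives 23.0 against 7.0 per 100 PY (ratio 3.3), or 12.6 against 5.9 (ratio 2.2). The uptake curve does not support the contrast, because it gives NOAC users about two years on average.

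Nor do the documents say that the hazard falls after VTE. Section 7 says that risk varies over the disease and is highest after chemotherapy starts, in cancer patients generally. It says nothing on time since VTE. Finally, no comparison of classes is planned, so the harm arises only if readers set the rates side by side. Section 9 does not invite that, although the rationale says that the evidence should support treatment decisions.

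**Conclusion.** The point on Objective 4 holds. It needs only what the protocol states, a rise in NOAC use over time, to conclude that a pooled share lies below current use. Its size rests on assumed uptake: the pooled share is about a third to a half of the 2017 share in the scenarios shown.

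The point on Objectives 5 and 7 is secondary and conditional. It applies to the definition running to the end of follow-up, before duration strata, and only if the hazard falls after VTE. On the hazards tried with the main uptake curve, the artefact is a ratio of about 1.2 to 1.4. It vanishes under a constant hazard. The documents do not support a claim that class rates will differ because of follow-up length whatever the hazard. Overall this is an inexpensive improvement to a descriptive study and does not invalidate it.

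**What to change.** 1. In section 9.8, tabulate Objective 4 by calendar period of the index VTE, for example 2007–2011, 2012–2014 and 2015–2017. State that the latest period answers the current-landscape aim, and keep the pooled table as a description of the whole period.
2. For Objectives 5 and 7, also report class-specific rates in fixed windows since the index VTE: 0–3, 3–6, 6–12 and over 12 months. With equal hazards within a window, classes then show equal rates whatever their follow-up. The last window is open-ended, so this holds there only if the hazard is flat by then.
3. When setting the latest calendar period, use one end date; sections 9.2.3 and 9.4.1 differ by two months.

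The data are already held. The cost is more table rows, smaller cells and wider intervals, most of all for recent periods and late windows.

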Data analysis	
Among men with PCa:
 
Descriptive statistics will be used to define the socio-demographic and clinical characteristics of all PCa patients at the date of incident PCa diagnosis (baseline) as well as main types of cancer therapies.
 
The occurrence (incidence rate) of cancer-related VTE events, split into PE and DVT events will be also described by Kaplan-Meier curves in different strata.
 
The anticoagulation (AC) treatment received by the PCa patients after the first cancer-related VTE event at an out-patient long-term basis will be reported by type of anticoagulation (LMWH, VKAs and NOACs) and its estimated duration (up to 3 months, 3-6 months, more than 6 months). Among this sub-group of patients, the occurrence (incidence rates) of recurrent VTE and the time to recurrence, post-VTE bleeding leading to hospitalisation, and mortality will be calculated by the type and duration of AC treatment.
 
Among PCa-free men:
 
Descriptive statistics will be used to define the socio-demographic and clinical characteristics of PCa-free men at the time of inclusion in PCBaSe (baseline).
 
The occurrence of VTE events, split into PE and DVT events will be also described by Kaplan-Meier curves in different strata.

Milestones	The project is planned to begin in May 2019 and will end in April 2020.

5. Amendments

<None>

6. Milestones

Table 1: Milestones

Milestone	Planned date
Study start	May 2019
Submission of application form for approval from Research Ethics Board Uppsala	March 2019
Development of a study file containing the data	June 2019
Upload study file Research Platform	June 2019
Registration in the EU PAS register	April 2019
Study end	December 2019
Final report of study results	April 2020

7. Rationale and background

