8.1 Primary objective

Among all men with PCa:

- To describe socio-demographic and clinical characteristics at the date of an incident PCa diagnosis.
- To estimate the occurrence of cancer-related VTE.
- To describe the cancer therapies in PCa at the initial time after diagnosis.

Among men with PCa and a first cancer-related VTE event:

- To characterize the long-term anticoagulation treatment including choice of drug and duration of treatment.
- To estimate the occurrence of recurrent VTE events by long-term anticoagulation treatment (LMWH, VKA or NOAC) and its estimated duration (up 3 months, 3-6 months, more than 6 months).
- To determine the time between a first cancer-related and a recurrent VTE event.
- To estimate the incidence rates of post-VTE bleeding events leading to hospitalization, and mortality by anticoagulation treatment.

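### Mortality rates by achieved anticoagulation duration, with time at risk counted from the VTE, favour long treatment even if duration has no effect; the recurrence and bleeding rates share the selection

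*Protocol*

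**What the plan says.** Section 9.8 fixes the clock and the strata for the outcomes after VTE.

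- **Start:** "Time at risk for Objectives 5, 6 and 7 (recurrent VTE, bleeding leading to hospitalisation or death) will be calculated from first cancer-related VTE".
- **End:** "for each events of interest up until event, death or end of follow-up".
- **Strata:** "Incidence rates of recurrent VTE, bleedings and death will be calculated by the type and duration of AC treatment (stratification variables").
- **Duration bands:** for the description of treatment, 9.8 gives "its estimated duration (from the time-point of a hospital discharge up to 3 months, 3-6 months, more than 6 months").

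In section 8.1, the recurrence objective (Objective 5 in the abstract) asks for rates by drug "and its estimated duration (up 3 months, 3-6 months, more than 6 months"). The bleeding and mortality objective (Objective 7) does not mention duration: "To estimate the incidence rates of post-VTE bleeding events leading to hospitalization, and mortality by anticoagulation treatment". Duration is added for those outcomes by 9.8 and by the abstract's data analysis row, which says that "mortality will be calculated by the type and duration of AC treatment".

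The end of treatment comes from later dispensing records (9.4.3). Under the refill-interval method, treatment ends three months after the last fill. Section 9.4.1 defines exposure in two ways: follow-up to the end of observation regardless of treatment, and follow-up only while on treatment. No section describes a landmark, a split of person-time by time on treatment, or time-updated duration.

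**The concern.** Achieved duration is known only after follow-up has run, yet 9.8 uses it to stratify person-time that begins at the VTE. Every man in the stratum above 6 months brings an early stretch in which he could not have died and still been classified there. A man who dies in month 2 can never enter that stratum, whatever treatment was intended for him. This is immortal-time bias.

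Section 7 says that reliable data on anticoagulation beyond 6 months in cancer patients are lacking, and that the evidence generated will support treatment decisions. A mortality table that favours long treatment by construction would speak to exactly that gap. The distribution of durations under Objective 4 is not affected.

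**Working it through.** **Inputs from the protocol.** Time zero is the VTE. Time ends at event, death or end of follow-up. The cut points are 3 and 6 months. The protocol gives no rate or duration figure for this sub-population, so there is no planned figure to reproduce.

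**Assumptions.** The death rate λ is constant and the same for every man. Intended duration is independent of death. Achieved duration is the smallest of intended duration, time to death and end of follow-up. Any gradient across strata is then an artefact.

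**Step 1: the long stratum in closed form.** Let every man have the same maximum follow-up of F years. A man in the stratum above 6 months has survived 0.5 year and then dies at rate λ for up to F − 0.5 years.

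- Deaths per man: d = 1 − exp(−λ(F − 0.5))
- Person-years per man: 0.5 + d/λ
- Reported rate: d / (0.5 + d/λ), which is always below λ

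With λ = 0.10 and F = 5: d = 1 − exp(−0.45) = 0.3624; person-years = 0.5 + 3.624 = 4.124; rate = 0.3624 / 4.124 = 8.79 per 100, against a true 10.

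With λ = 0.40 and F = 5: d = 1 − exp(−1.8) = 0.8347; person-years = 0.5 + 2.087 = 2.587; rate = 32.27 per 100, against a true 40.

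Under these assumptions, the deficit in the long stratum does not depend on the assumed mix of durations.

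**Step 2: all three strata by simulation.** Exponential intended duration with median 6 months, 2,000,000 men per scenario, clock as in 9.8, deaths per 100 person-years:

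| True rate | Follow-up | Up to 3 | 3-6 | Over 6 months | Short/long |
|---|---|---|---|---|---|
| 10 | 5 years | 11.45 | 10.83 | 8.79 | 1.30 |
| 10 | 2 years | 13.25 | 11.68 | 7.37 | 1.80 |
| 40 | 5 years | 50.00 | 43.74 | 32.27 | 1.55 |
| 40 | 2 years | 55.44 | 46.01 | 27.72 | 2.00 |

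The 5-year entries for the long stratum equal the closed-form values. No death before 6 months fell in the long stratum in any scenario.

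**Step 3: a second duration mix with staggered follow-up.** Intended duration is 1-3 months in 25% of men, 3-6 in 35% and 6-36 in 40%. Follow-up is uniform from 0.05 to 10.8 years.

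| True rate | Follow-up rule | Up to 3 | 3-6 | Over 6 months | Short/long |
|---|---|---|---|---|---|
| 10 | 9.8 as written | 11.8 | 10.0 | 8.9 | 1.3 |
| 30 | 9.8 as written | 38.5 | 29.8 | 24.6 | 1.6 |
| 10 | same strata, on-treatment (9.4.1) | 49.4 | 10.2 | 6.8 | 7.3 |
| 30 | same strata, on-treatment (9.4.1) | 135 | 28.7 | 19.5 | 6.9 |

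**Step 4: does the remedy work?** In the step 2 setting (true 10, 5 years), time-updated duration returned 9.93 / 9.95 / 9.97, and a 6-month landmark returned 9.98 / 10.05 / 10.00. In the step 3 setting (true 30), time-updated duration returned about 30 in every band.

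**Step 5: the three-month extension in 9.4.3.** The protocol does not say whether the three months added after the last fill are cut at death. If they are cut, every death before month 3 falls in the shortest stratum. If they are not, then with assumed monthly fills about 66% of those deaths fall in the 3-6 month stratum; with three-monthly fills none do. No early death reached the long stratum either way, and the gradient remained.

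**The case against.** **The allocation of person-time could be left to the SAP.** Section 9.8 does not say in terms that each man receives one final label, and 9.4.1 already plans censoring at switching and discontinuation. That is fair as far as it goes. But the protocol itself fixes the VTE as time zero, fixes the end of follow-up and names duration as a stratification variable. Followed literally, it gives the biased rates; a SAP that repaired them would be departing from 9.8.

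**The study is descriptive and 9.8 plans no comparative analysis.** That sentence covers the three drug groups. It does not correct the rates by duration, each of which is off as a description. Section 9.10 does not mention the problem, although checklist item 7.3, which gives time-related bias as an example, is ticked yes and refers there.

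**Three stronger readings are tempting and not supported.**

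- A reader might infer that early deaths can fall only in the shortest stratum. That holds only if duration is cut at death (step 5). What is firm is that the long stratum requires survival and a later fill.
- A reader might infer that recurrence rates are biased against long treatment because a recurrence prompts more fills. The protocol contains nothing on such re-treatment, 9.4.3 starts a new treatment period for a refill after more than six months, and 9.4.1 lists recurrence among its censoring events.
- A reader might take the roughly sevenfold on-treatment ratio as the size of the error. It combines the strata of 9.8 with the follow-up of 9.4.1; the rule written in 9.8 gives the smaller ratios.

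**Conclusion.** The rule in 9.8 and the abstract is wrong as written for mortality by duration. The direction follows from the text: the long stratum is favoured and early deaths are pushed into the shorter ones. The size rests on assumed death rates, durations and follow-up. Under the 9.8 clock the short-to-long ratio was about 1.3 to 1.6 with staggered follow-up, and up to 2.0 with only 2 years of follow-up, where the true ratio is 1. It was about 7 if on-treatment follow-up is used with the same strata.

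Recurrence and bleeding rates by duration carry the same survival selection, because the men in the long stratum must have survived. Early events of these kinds need not end treatment, so they are not confined to the short stratum, and the event may itself change later dispensing. Neither the size nor the net direction can be derived from the protocol.

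**What to change.** Change 9.8 and the abstract together.

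1. **Make duration time-updated.** Split each man's person-time into 0-3, 3-6 and more than 6 months on treatment, plus off treatment. Assign each event to the state current on its date. Ignore dispensings on or after the outcome date when computing duration.
2. **Or use landmarks at 3 and 6 months.** Take men alive and event-free at the landmark, group them by treatment up to that point, and start follow-up there.
3. **Objective 7:** use the same split, or drop duration, since 8.1 asks only for rates by treatment.
4. **Any rate by drug type:** start time at risk at the first dispensing, or count the time from VTE to first dispensing as untreated. Otherwise that interval is immortal too, and dropping duration does not remove it.

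The cost is wording and some programming, with no new data. Under the landmark version, early events appear only in the overall early rate. Time-updated bands still reflect time since VTE: with an assumed death rate of 60, 30 and then 15 per 100 person-years falling over time and no duration effect, they returned 59.8 / 29.8 / 15.0. The report should say that the bands are not effects of duration.
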